Relative Mitochondrial Toxicity of Tenofovir Alafenamide (TAF) vs. Tenofovir Disoproxil Fumarate (TDF)

Identifiers: NCT03251144

March 22, 2022

STUDY SCHEMA

HIV infected participants on stable antiretroviral therapy will be switched to newer antiretrovirals to evaluate the effect of these newer antiretrovirals on mitochondria.

Primary Objective(s) Primary Endpoint(s)
	
To assess in vivo the effects of TAF on mitochondrial health as assessed by several assays. Primary outcome will be cellular oxygen consumption (COC) and secondary outcomes the rest of measures of mitochondrial health as described in the study design.

Study Regimen/Intervention
	
There are 3 scenarios based on the possible TAF-based regimens
 
A) Scenario 1: TAF based regimen is Stribild Study Switch (Stribild→ Genvoya. Intervention: Genvoya (elvitegravir 150 mg/cobicistat 150 mg/emtricitabine 200 mg/tenofovir alafenamide 10 mg; E/C/F/TAF)
 
Emtricitabine 200 mg/tenofovir alafenamide 25 mg; E/C/F/TAF 1 tablet orally once daily.
 
Optional switch to expedite recruitment (see study design) (any other ART → Stribild): Intervention: Stribild®; (elvitegravir 150 mg/cobicistat 150 mg/emtricitabine 200 mg/tenofovir disoproxil fumarate 300 mg; E/C/F/TDF) 1 tablet orally once daily.
 
B) Scenario 2: TAF based regimen is ODEFSEY Study Switch (Complera (Emtricitabine/Rilpivirine/Tenofovir Disoproxil Fumarate Tablets) → ODEFSEY® (emtricitabine, rilpivirine, and tenofovir alafenamide). Intervention: ODEFSEY (25 mg rilpivirine + 200mg emtricitabine + 25mg tenofovir alafenamide fumarate) 1 tablet orally once daily.
 
C) Scenario 3: TAF based regimen is Descovy Study Switch (TRUVADA (emtricitabine/tenofovir disoproxil fumarate) + any other combination of antivirals --> Descovy (tenofovir alafenamide + emtricitabine) + any other combination of antivirals. Intervention: Descovy (200 mg emtricitabine + 10 mg tenofovir alafenamide fumarate) 1 tablet orally once daily.
 
After any ART switch safety labs will be done within 2 months (will aim for 1 month post switch)

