vs TDF on mitochondria. The participants who will undergo any ART switch will have a clinic visit or a phone call 1-2 weeks after the ART switch to check for side effects/tolerability of the new regimen and all subjects will have a clinic visit with blood tests to check viral load and safety labs (complete metabolic panel and complete blood count) within 2 months after any switch. Then after informed consent has been obtained ART will be switched as per protocol.

During visits at baseline, month 2, 6, blood will be obtained for isolation of PBMC (measurement of mitochondrial function). This study design will account for confounders that may affect mitochondrial function among different subjects (given the intrinsic heterogeneity of mitochondria). All study participants will be recruited in outpatient clinics within UCLA. All HIV-1 infected participants will be recruited within the UCLA Center for AIDS Education and Research (UCLA CARE) Center which provides HIV care to over 1000 patients with HIV in Los Angeles and is regarded as one of the premier HIV care providers in the country. We anticipate recruiting 60 (30 HIV-1 infected and 30 uninfected) persons in total for all outlined experiments.

STUDY POPULATION

HIV-1-infected participants in the Los Angeles area will be recruited voluntarily through a UCLA IRB-approved protocol at UCLA Center for AIDS Research and Education (CARE).

Enrollment will be open to men and women from all socioeconomic strata and all race and ethnic groups. We anticipate enrolling 30 HIV-1 infected individuals in total.

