Day -60 or up to -30: Follow up visit within 2 months after visit 0 (optional): Safety and early effects of Stribild (safety labs) will be assessed.

Day 0: Baseline visit: prescription given for Genvoya; begin switch from TDF based regimen to TAF based regimen.

Day 60 (2 month follow up visit): Safety follow-up and early (2 month post switch) differential in vivo effects of TAF based regimen on mitochondrial health will be assessed.

Day 180 (6 month follow up visit): Late (6 month post switch) differential in vivo effects of TAF based regimen on mitochondrial health will be assessed.

Blood draws will be done at Day -90, Day 0, Day 60, Day 180 for laboratory testing. Approximately 100mL will be collected at each visit, with no more than 400 mL total over the course of the study.

Screening

Medical records will be accessed and reviewed for:

- HIV status (e.g. CD4 count, viral load)
- Age
- Underlying condition and comorbidities
- Medications
- Labs e.g. creatinine to determine kidney and liver function

Switch to Stribild: switch from any other ART→Stribild. No additional blood draw.

Participants will undergo a blood draw (100mL) and then be given a prescription for TAF based regimen for 6 months (switch from TDF→TAF).

Entry/Day 0

Follow-up phone call

2 weeks after the Entry visit, a brief phone call from the PI or study coordinator will be made to participants to ensure they are adjusting to the switch okay. The following questions will be asked:

- Are you tolerating the new medication okay?
- Have you experienced any new symptoms since you started the new drug? (expected side effects from switching antivirals should have already been addressed at the initial study visit).
- Have you been taking all your pills?
- Do you have any questions we could answer for you?

If new symptoms appear, the participant will be instructed to schedule a visit with their care provider for standard evaluations.

Day 60 post-switch
Blood draw (100mL)

Day 180 post-switch
Blood draw (100mL)

Laboratory Evaluations

Mitochondrial function assays: The Seahorse method measures function through the COC (increased COC indicates reduced bioenergetic capacity and mitochondrial dysfunction).

Specimen Preparation, Handling and Shipping

Whole blood will be collected using standard phlebotomy and placed in standard heparin green top tubes. All tubes per participant will be placed in a biohazard bag and shipped at room temperature to [name] Lab for further processing.

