Ship to: [name] Lab/Infectious Diseases
[name]
[name]

Total Blood Volume

100 mL of blood will be collected during Day -90, Day 0, Day 60, and Day 180. No more than 400mL of blood will be collected for this study.

CARE Clinic will draw and collect blood to be sent to [name] lab via courier. [name] lab will handle all blood processing, including peripheral blood mononuclear cells (PBMCs),

Entry visit

- Fasting Lipid Profile

The following labs are to be done only if they have not been done within the last 3 months:

- CBC
- Complete metabolic panel
- HIV RNA PCR
- CMV antibody

Safety labs for Visit 2:

- HIV viral load
- T-cell subset
- CBC
- CMP
- Fasting Lipid Profile
-

Safety labs for Visit 3:

- CBC
- CMP
- Fasting lipid profile

100 ml of blood will be drawn per visit/phlebotomy. Out of this volume standard tubes for the standard clinical

labs (fasting lipid profile, complete metabolic panel, HIV RNA PCR, CMV antibody, T- cell subset) will be sent to the clinical laboratory as per standard clinic procedure. The rest of the whole blood will be placed in EDTA or green top tubes and will be shipped to [name] lab via courier. It is expected that 1 million cells will be obtained per ml of whole blood and cells will be isolated and cryopreserved at [name] lab.

ASSESSMENT OF SAFETY

Adverse Event Reporting and monitoring.

An AE is any unfavorable and unintended sign (including an abnormal laboratory finding), symptom, or diagnosis that occurs in a study participant during the conduct of the study REGARDLESS of the attribution (i.e., relationship of event to medical treatment/study product/device or procedure/intervention). This includes any occurrence that is new in onset or aggravated in severity or frequency from the baseline condition. The Division of AIDS Table for Grading the Severity of Adult and Pediatric Adverse Events (DAIDS AE Grading Table), corrected Version 2.1, July 2017, must be used for grading the adverse events in this protocol and is available on the DAIDS RSC Web site at <http://rsc.tech-res.com/clinical-research-sites/safety-reporting/daids-grading-tables>.

The AEs/SAEs should immediately be reported to the Principal Investigator. All events should be reported to the local IRB if they are reportable per the local IRB's reporting criteria.

This study will be internally monitored biannually.

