A Data Safety Monitoring Board is not needed for this single-center open-label Phase I clinical trial (safety related to mitochondrial toxicity) since the local investigator will have access to all data. [name] will be available to provide direct evaluation of any clinically-related concerns that might arise during the study. The principal investigator will directly discuss with assigned independent persons appointed by Gilead any concerns for adverse events (mitochondrial toxicity) and make recommendations for continuing or stopping the study. It is important to emphasize that the clinical safety of the described antiretrovirals has already been established within large scale clinical trials. This exploratory study will investigate subtle molecular readouts of mitochondrial toxicity that have been associated with adverse clinical outcome in some settings (e.g. diabetes). However the exact clinical significance of the findings from this small exploratory study will need to be validated in further larger scale trials. Thus, given the nature and scope of this study we do not anticipate any major clinical side effects and stopping the study early if subtle effects of antiretrovirals on mitochondria are detected.

CLINICAL MANAGEMENT

Not Applicable.

Criteria for Discontinuation

The study may be discontinued at any time by the IRB, OHRP, or other government agencies when necessary to ensure the protection of research subjects.

Completion of study product(s)/intervention(s) as defined in the protocol

Criteria for Premature Study Discontinuation for an Individual Participant

- Participant repeatedly non-compliant with study product/intervention as prescribed
- Pregnancy or breastfeeding
- Request by participant to withdraw
- Participant judged by the investigator to be at significant risk of failing to comply with the provisions of the protocol as to cause harm to self or seriously interfere with the validity of study results
- Participants will be taken off of study in the event of virologic failure or in the event of grade 3 or higher adverse effects or intolerable grade 2 adverse effects

STATISTICAL CONSIDERATIONS

Study Endpoints

Primary Endpoint

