Cellular oxygen consumption (COC): From all the measures of mitochondrial function **cellular oxygen consumption (COC)** will be considered the “gold standard” given it is a measure of the most important mitochondrial function (oxidative phosphorylation) that relates to clinical outcome. It is accepted that two independent measures of mitochondrial function can more reliably predict mitochondrial dysfunction compared to each one of the measures separately. Thus, given the uncertainty of what measure of mitochondrial function can best predict NRTI-induced mitochondrial toxicity, comparison of relative fold induction of mitochondrial dysfunction in PBMC compared to baseline measurement will be done.

Primary endpoint is continuous variables (measured in pmoles O₂/min) and it will be compared between the 2 groups on different antiretrovirals (TAF based vs TDF based) cross sectionally using unpaired t-test. Changes in primary outcome within the same person will be determined by paired t-test (baseline and after switch). Statistical p value <0.05 will be considered statistically significant.

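### The paired COC test names no post-switch visit; if Day 180 is meant, participants removed earlier drop out and their Day 60 values go unused

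*Combined protocol and SAP*

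**What the plan says.** **Removal.** Under Criteria for Premature Study Discontinuation for an Individual Participant: "Participants will be taken off of study in the event of virologic failure or in the event of grade 3 or higher adverse effects". The same bullet adds grade 2 effects that the participant cannot tolerate. Other bullets cover non-compliance, pregnancy or breastfeeding, and withdrawal at the participant's request.

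**Sampling.** Study Design: "During visits at baseline, month 2, 6, blood will be obtained for isolation of PBMC (measurement of mitochondrial function". Schedule of Events: "Blood draws will be done at Day -90, Day 0, Day 60, Day 180 for laboratory testing". After the TDF-to-TAF switch, COC is therefore scheduled only at Day 60 and Day 180. No draw at removal and no sampling after it is listed.

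**Analysis.** Statistical Considerations, Primary Endpoint: "Changes in primary outcome within the same person will be determined by paired t-test (baseline and after switch", judged at p < 0.05. The text does not say which post-switch visit is meant. It gives no analysis population, no rule for missing values and no model that uses both post-switch visits.

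**Direction.** Laboratory Evaluations: "increased COC indicates reduced bioenergetic capacity and mitochondrial dysfunction". A rise after the switch is thus the unfavourable result.

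**The concern.** A paired test needs both members of the pair. With Day 180 as the second member, a participant removed at or after Day 60 but before Day 180 is excluded although a post-switch COC value exists. With Day 60 as the second member, only removals before that draw lose a pair. The plan does not choose, and in an open-label study the choice should be fixed before COC results are seen.

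Two things are at stake. The first is precision, because data already collected are discarded. The second is selection. The study measures a marker of mitochondrial toxicity and removes people for adverse effects. If those removed tended to have rising COC, the remaining month-6 mean would lean towards a favourable reading of TAF: power would fall against a true worsening and rise against a true improvement. If removal went with falling COC, the lean would reverse.

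**Working it through.** **1. Who would lack which value.** That a removed participant gives no later sample is inferred from the wording and the schedule; it is not stated.

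| Removal | Day 0/60 pair | Day 0/180 pair |
|---|---|---|
| Before the Day 60 draw | lost | lost |
| On Day 60 findings, or between Day 60 and Day 180 | kept | lost |
| On Day 180 findings | kept | kept |

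A lone Day 60 value is a realistic pattern: HIV viral load is in the Visit 2 safety labs and not in the Visit 3 list, so a failure found at Visit 2 leaves Day 0 and Day 60 values only. Earlier removal is also possible. The Study Schema says "After any ART switch safety labs will be done within 2 months (will aim for 1 month post switch", and new symptoms reported at the two-week call lead to a care-provider visit; neither has a COC draw attached.

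**2. Inputs.** From the documents: n = 30 and alpha 0.05. Assumed: two-sided test, a true effect of 0.5 SD of the paired change, k = 1 or 3 removals, correlation rho of 0.2 to 0.5 between the tendency to be removed and the Day 180 change, and correlation 0.6 between Day 60 and Day 180 changes. The plan states no power, SD, effect size or dropout, so it has no figure to reproduce.

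**3. Loss of numbers alone.** The noncentral t distribution with noncentrality 0.5 × √n gives power of 75.4% (n = 30), 73.9% (29) and 70.6% (27). The standard error is 1/√n: 0.183 SD at n = 30 and 0.192 SD at n = 27.

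**4. Selective loss, Day 180 test.** Removing the k largest of 30 normal values shifts the mean by -0.07 SD (k = 1) or -0.185 SD (k = 3). If the k highest on a score correlated rho with the change are removed, bias = rho × that shift:

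- k = 1: 0.2 × -0.07 = -0.014; 0.5 × -0.07 = -0.035
- k = 3: 0.2 × -0.185 = -0.037; 0.5 × -0.185 = -0.093

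Simulation (60,000 to 200,000 trials per scenario) agrees:

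| k, rho | Bias (SD) | False fall in COC | False rise in COC | Power, worsening | Power, improvement |
|---|---|---|---|---|---|
| 0 | 0 | 2.5% | 2.5% | 75% | 75% |
| 1, 0.2 | -0.014 | 2.9% | 2.2% | 71.6% | 76.4% |
| 1, 0.5 | -0.034 | 3.9% | 1.7% | 68.9% | 80.3% |
| 3, 0.2 | -0.037 | 3.9% | 1.5% | 64.2% | 77.0% |
| 3, 0.5 | -0.092 | 7.3% | 0.9% | 56.0% | 86.0% |
| 3, -0.2 | +0.039 | 1.7% | 4.0% | 77.4% | 63.9% |

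**5. Separating the two effects, k = 3.** Ordinary loss of numbers costs 75.4 - 70.6 = 4.8 points of power for worsening. Selection costs a further 70.6 - 64.2 = 6.4 points at rho 0.2, or 70.6 - 56.0 = 14.6 points at rho 0.5.

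**6. What a repeated-measures model recovers (k = 3, rho 0.5).**

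- All removed after Day 60, removal dependent on Day 60 COC: bias goes from -0.055 to 0.00 SD, and power for worsening from 61.5% to 72.7%.
- All removed after Day 60, removal dependent on the unseen Day 180 value: -0.092 to -0.059 SD, and 56.0% to 62.7%. The remaining bias is -0.084 SD if the Day 60/Day 180 correlation is 0.3 and -0.034 SD if it is 0.8.
- One removed before, one at and one after Day 60: -0.056 to -0.018 SD (Day 60-dependent) or -0.094 to -0.071 SD (Day 180-dependent).
- All removed before Day 60: no gain.

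This was a random-intercept model on change from baseline with equal variances and correlations, a favourable case for the model.

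**The case against.** A reader might infer that the plan commits to a completers-only analysis. It does not. The Schedule of Events describes an early assessment at Day 60 and a late one at Day 180. If each is tested, a person removed after Day 60 still counts in the early comparison. The exclusion follows only for a Day 180 pairing. This stands, and it is why the unnamed visit comes first.

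A reader might also infer that removals will make TAF look less toxic. The documents do not support that. They link none of the removal criteria to COC, they count adverse events whatever their cause, and they anticipate no major clinical side effects. At assumed removal risks of 2%, 5% and 10%, the chance of three or more removals among 30 is 2%, 19% and 59%. If only one of three removals is related to COC (rho 0.5), bias is about -0.035 SD and total type I error 5.6%. At rho 0.2 with three removals, total error is 5.4%. These points stand and keep the concern minor.

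The timing of early removals is uncertain too: the Schedule of Events lists no one-month visit after the TAF switch, so safety findings may mostly arise at Day 60, where COC is drawn.

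Finally, the model helps least where selection is worst. That is true, but it uses data already in hand and does not depend on removal being frequent.

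**Conclusion.** The gap is real and of minor importance. The plan leaves open which visit the primary paired comparison uses and what becomes of a lone Day 60 value. Under a Day 180 pairing, one removal has a small effect and three could matter: a bias of about 0.04 to 0.09 SD, or 0.2 to 0.5 of the standard error at n = 27 (0.037/0.192 and 0.092/0.192).

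These sizes depend on the assumed number of removals, rho and effect size; the sign depends on an unknown relation between removal and COC. If removal is unrelated to COC, three removals cost about 5 points of power and cause no bias. Under a Day 60 pairing, only removals before that draw matter.

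**What to change.** Leave the clinical criteria unchanged and amend Statistical Considerations:

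1. Name the post-switch time point of the primary within-person comparison, Day 60 or Day 180.
2. Analyse all participants with a baseline and at least one on-TAF post-switch COC value in a repeated-measures model using Day 0, Day 60 and Day 180, with the primary result being the change at the named visit. Keep the paired t-test as a sensitivity analysis.
3. Report removals by number, timing and reason.

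The cost is a few sentences and slightly more analysis work, with no new samples. The model removes the bias only if data are missing at random given the observed COC, and it recovers nothing for participants removed before Day 60; the report should say so.

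I do not recommend an added COC draw at removal. It would take up to 100 mL from someone who would otherwise give no further sample, and a value taken off TAF would not fit the on-TAF analysis in step 2.

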
Study Duration
	
There are a total of 3-5 study visits over a period of up to 9 months.
 
Visit 0: (Optional) If not on Stribild, participant will switch from their current ART→ Stribild. Must stay on Stribild for 3 months before starting Visit 1.
 
Safety labs visit 0: Follow up visit within 2 months after visit 0 (optional): Safety and early effects of Stribild (safety labs) will be assessed.
 
Visit 1: Baseline visit: participant switched from TDF based regimen to TAF based regimen. A follow-up phone call will be made ~2 weeks after Entry.
 
Visit 2: 2 month follow up visit: Safety and early effects of TAF based regimen on mitochondrial health will be assessed.

	Visit 3: 6 month follow up visit: differential in vivo effects of TAF based regimen on mitochondrial health will be assessed.
Study Population	
30 participants will be enrolled
 
Eligibility criteria:
 
 ● 18 years of age or older ● HIV infected and on anti-retroviral therapy with suppressed viremia for at least 3 months (viral RNA <50 copies per ml) ● On stable antiretroviral therapy for ≥ 6 months with TDF based regimens: 1) Stribild®; elvitegravir 150 mg/cobicistat 150 mg/emtricitabine 200 mg/tenofovir disoproxil fumarate 300 mg; E/C/F/TDF) OR 2) Complera (Emtricitabine 200 mg /Rilpivirine 25 mg/Tenofovir Disoproxil Fumarate 300 mg Tablets OR 3) Truvada (Emtricitabine 200 mg /Tenofovir Disoproxil Fumarate 300 mg Tablets ● On stable antiretroviral therapy for ≥ 6 months with ANY OTHER than Stribild antiretroviral therapy and willing to switch to Stribild for at least 3 months. This optional switch (switch 1: old ART regimen to Stribild) will expedite recruitment and study completion (see study design). Once on 3 months of Stribild these participants would be eligible for switch from Stribild to Genvoya as described in the study design. ● Adequate renal function determined by the Cockcroft-Gault formula for creatinine clearance (>60 mL/min/1.73 m²) ● Able and willing to communicate in English ● Able and willing to provide written consent

STUDY DESIGN

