An open-label switch study will be conducted in virologically-suppressed, HIV-1 positive participants. The switch regiment will be: 1) Stribild®; elvitegravir 150 mg/cobicistat 150 mg/emtricitabine 200 mg/tenofovir disoproxil fumarate 300 mg; E/C/F/TDF) to Genvoya; elvitegravir 150 mg/cobicistat 150 mg/emtricitabine 200 mg/tenofovir alafenamide 10 mg; E/C/F/TAF OR 2) Complera (Emtricitabine/Rilpivirine/Tenofovir Disoproxil Fumarate Tablets) to ODEFSEY (25 mg rilpivirine + 200mg emtricitabine + 25mg tenofovir alafenamide fumarate) OR 3) TRUVADA (emtricitabine/tenofovir disoproxil fumarate) + any other combination of antivirals to Descovy (200 mg emtricitabine + 10 mg tenofovir alafenamide fumarate).

Major eligibility criteria for study participants will be age > 18 years old, any CD4 T cell count, viral load <50 copies/ml or undetectable on E/C/F/TDF for the previous 3 months prior to the onset of study, adequate renal function determined by the Cockcroft-Gault formula for creatinine clearance and no evidence of acute hepatitis in the prior 30 days. Major exclusion criteria will be pregnancy and diseases or use of other drugs known to affect mitochondrial function. Subjects will have three clinical visits: one at baseline prior to the TDF to TAF switch, and follow up visits at 2 and 6 months after the switch. We will also include the option to switch ANY HIV-infected person who meets the inclusion criteria and not on an antiretroviral regimen other than Stribild [(Elvitegravir (ELV)/cobicistat (CO)/emtricitabine (FTC)/tenofovir (TDF)] to switch to Stribild for 3 months. This will allow for future switch (after these 3 months) from Stribild to GENVOYA. This approach can expedite recruitment since we can switch HIV infected persons to Stribild and then do another switch from Stribild to GENVOYA as per study protocol. In addition given the known clinical benefits (less toxicity) of Stribild and Complera compared to older antiretrovirals (such as protease inhibitors) [Patient Prefer Adherence. 2015; 9: 1213–1218.; J Acquir Immune Defic Syndr. 2014 Mar 1; 65(3):e118-20; Lancet. 2012 Jun 30;379(9835):2439-48; J Acquir Immune Defic Syndr. 2014 Mar 1; 65(3):e121-4; AIDS. 2012;26:2315–2326; J Infect Dis. 2015;212(3):345–354] and the known clinical benefits of TAF compared to TDF (less bone and kidney toxicity) these ART switches are beneficial for the participant and they also allow us to study differential effects of TAF

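### The primary endpoint has an unpaired and a paired t-test with no ranking, and the unpaired TAF vs TDF test does not fit a design in which the same people supply both values

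*Combined protocol and SAP*

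**What the plan says.** The Primary Endpoint text under Statistical Considerations gives two tests for COC. Of the endpoint it first says "it will be compared between the 2 groups on different antiretrovirals (TAF based vs TDF based) cross sectionally using unpaired t-test". The next sentence reads "Changes in primary outcome within the same person will be determined by paired t-test (baseline and after switch", with no visit specified. A single significance threshold of 0.05 follows, with no order, split or hierarchy. The preceding paragraph also mentions a fold-type comparison with baseline, without attaching a test to it.

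The design sections describe one switched cohort:

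- The Study Schema states "30 participants will be enrolled".
- Study Design gives the visits as "one at baseline prior to the TDF to TAF switch, and follow up visits at 2 and 6 months after the switch".
- The Day 0 entry in the Schedule of Events reads "begin switch from TDF based regimen to TAF based regimen".
- Study Design says of the assays: "During visits at baseline, month 2, 6, blood will be obtained for isolation of PBMC (measurement of mitochondrial function".
- Study Design gives the rationale: "This study design will account for confounders that may affect mitochondrial function among different subjects (given the intrinsic heterogeneity of mitochondria".

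The only other people mentioned appear in Study Design: "We anticipate recruiting 60 (30 HIV-1 infected and 30 uninfected) persons in total for all outlined experiments". The uninfected persons are given no TDF or TAF regimen, no visit and no analysis.

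**The concern.** An unpaired t-test requires two independent samples. Here the TDF sample and the TAF sample are two visits of the same people. Participants who enter through the optional Stribild lead-in also go on to Genvoya, so they do not form a separate TDF group either.

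The unpaired test puts back into the error term the between-person variation that the switch design is meant to remove. It is also the test listed first and attached directly to the primary endpoint, so a reader could take it as the main analysis. If the two tests disagree, the plan does not say which result stands.

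Separately, COC is measured after the switch at both month 2 and month 6, and the plan does not say which of these decides the primary result.

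**Working it through.** **Inputs from the documents.** There are 30 switched participants (Study Schema), COC is measured at baseline, month 2 and month 6 (Study Design), and the significance level is 0.05 (Statistical Considerations). The plan gives no power, SD, effect size or within-person correlation, so it has no figure of its own to reproduce.

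**Assumptions.** All 30 complete, the data are normal with equal SD σ at both visits, tests are two-sided, and the true shift is 0.5σ where power is shown. The correlation ρ between two visits of one person is taken as 0, 0.3, 0.5 and 0.7.

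**Step 1: standard errors.** The true variance of the mean difference is 2σ²(1−ρ)/n. The unpaired test estimates 2σ²/n. Its standard error is therefore too large by a factor 1/√(1−ρ), for example 1/√0.5 = 1.41 at ρ = 0.5.

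**Step 2: paired power.** This follows from the noncentral t distribution with 29 df and noncentrality 0.5·√30/√(2(1−ρ)), which is 1.94, 2.31, 2.74 and 3.54 for the four values of ρ.

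**Step 3: unpaired error, unpaired power and disagreement.** These come from simulation with 400,000 replicates per setting, both tests being run on the same data (58 and 29 df).

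| ρ | SE factor, unpaired | Type I error, unpaired | Power at 0.5 SD, unpaired | Power at 0.5 SD, paired | Opposite verdicts at 0.5 SD |
|---|---|---|---|---|---|
| 0 | 1.00 | 5.0% | 48% | 47% | 6% |
| 0.3 | 1.20 | 2.0% | 47% | 61% | 14% |
| 0.5 | 1.41 | 0.7% | 47% | 75% | 28% |
| 0.7 | 1.83 | 0.08% | 47% | 93% | 46% |

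From ρ = 0.3 upward almost every disagreement is paired significant and unpaired not: 13.8 of 14.1, 28.3 of 28.3 and 46.2 of 46.2 percentage points. With no true shift the tests disagree in 1.7%, 3.0%, 4.3% and 4.9% of trials.

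**Step 4: false positives from leaving the choices open.** At one visit, the chance that either test is falsely significant is 5.8% at ρ = 0 and 5.0% from ρ = 0.3 upward. If month 2 and month 6 are each tested by paired t-test at 0.05, the familywise error is about 9% (9.0% to 9.3% over this range of ρ, assuming the same correlation between all visits).

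**Step 5: after the fix.** One paired test with 30 people has 80% power for a mean change of 0.53 SD of the change. Multiplying by √(2(1−ρ)) gives 0.75, 0.63, 0.53 and 0.41 in units of σ.

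**The case against.** The strongest reply is that a valid analysis is already in the plan. The paired test is specified, and nothing says the unpaired result would prevail. The design rationale and the comparison with baseline in the same section both point to within-person change as the intended main comparison. The power gap is conditional on assumed values of ρ and the shift, and it vanishes at ρ = 0. Two unranked tests at one visit add almost no false-positive risk. The study also describes itself as small and exploratory, with findings to be validated in larger trials.

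Most of this stands as a limit on weight. It does not make the unpaired test valid for this design, and it does not name a primary test. The plan still declares a primary endpoint and a significance threshold.

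Two further points from that side also stand. The unnamed visit carries more false-positive risk than the choice of test. The schema and schedule call month 2 early, and the schedule calls month 6 late, but neither visit is called primary. The fold-type comparison with baseline leaves the scale of the analysis open as well.

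**Conclusion.** The concern holds and should be fixed. The unpaired test is wrong for the design as written, the two tests are not ranked, and the deciding visit is not named.

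The harm from the unpaired test is lost sensitivity, and it arises only if that result is relied on. Under the stated assumptions the loss runs from nothing at ρ = 0 to about 46 percentage points of power at ρ = 0.7 (93% against 47%). The harm from the open visit is a familywise error of about 9% instead of 5% if both visits are tested. Neither the correlation nor the size of shift comes from the documents, so these figures show a range and do not predict this trial.

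**What to change.** In the Primary Endpoint text:

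- Delete the unpaired TAF vs TDF t-test. If an independent TDF group was meant, define it and say when it is measured.
- Name the within-person paired comparison as the single primary test, at one follow-up visit (month 2 or month 6) that the sponsor chooses in advance. Make the other visit secondary.
- State whether change is analysed as a difference or as a ratio to baseline.

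Separately, state in Study Design which comparison, if any, the 30 uninfected persons serve.

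Deleting the unpaired test and naming the primary test, visit and scale costs wording only, with no new data and no new participants. Only the alternative of an independent TDF group would need participants whom the documents do not describe.
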